9 CONCOMITANT MEDICATIONS AND THERAPIES

9.1 Allowed Therapy

- Antiemetics and antidiarrheal medications are allowed prophylactically according to standard clinical practice if clinically indicated.
- Granulocyte colony-stimulating factors (G-CSF or GM-CSF) are allowed if used per clinical guidelines (eg, ASCO or ESMO guidelines).
- Bisphosphonates can be used to control bone loss or hypocalcemia if the benefit outweighs the risk per the investigator's discretion.

Note: osteonecrosis of the jaw has been reported in subjects using bisphosphonates (Section 8.3.1.3.8). Oral examinations are recommended at screening to determine eligibility and periodically during the study. In addition, subjects should be advised regarding oral hygiene practice and to quickly report symptoms to the investigator. Frequent monitoring for potentially overlapping toxicities with study treatment is recommended.

- Transfusions and hormone replacement should be utilized as indicated by standard clinical practice.
- Individualized anticoagulation therapy with heparin or direct factor Xa inhibitors rivaroxaban, edoxaban, or apixaban is allowed if it can be provided safely and effectively under the following circumstances:
 - *Low dose low molecular weight heparins (LMWH) for prophylactic use* are allowed if clinically indicated and the benefit outweighs the risk per the investigator's discretion.
 - *Therapeutic doses of LMWH or the direct factor Xa rivaroxaban, edoxaban, or apixaban at the time of the first dose of study treatment* are allowed if the subject has no evidence of brain metastasis, has been on a stable dose of anticoagulant for at least 1 week, and has had no clinically significant hemorrhagic complications from the anticoagulation regimen or the tumor.
 - *Low dose LMWH for prophylactic use after first dose of study treatment* are allowed if clinically indicated and the benefit outweighs the risk per the investigator's discretion.
 - *Therapeutic doses of LMWH or direct factor Xa inhibitors rivaroxaban, edoxaban, or apixaban after first dose of study treatment* are allowed if clinically indicated (eg, for the treatment of deep venous thrombosis), and the benefit outweighs the risk per the investigator's discretion. For management of thromboembolic complications while on study, refer to Section 8.3.1.3.4.
 - Accepted clinical guidelines regarding appropriate management while receiving any kind of anticoagulation therapy must be followed. This includes, but is not limited to, subject education regarding potential adverse drug reactions, monitoring laboratory parameters, dose adjustments (eg, due to kidney dysfunction). Caution is warranted in settings associated with an increased risk for bleeding such as gastrointestinal cancers, urothelial cancers, gastrointestinal mucosal abnormality (e.g., mucositis), renal or hepatic impairment, thrombocytopenia, arterial hypertension, or prior history of gastrointestinal bleed. For direct factor Xa inhibitors, the potential for drug-drug interaction with other concomitant medications, as well as gastrointestinal absorption, should be considered. Aspirin and other nonsteroidal anti-inflammatory drugs (NSAIDs) should not be used concomitantly with heparin or factor Xa inhibitors due

to the increased risk for bleeding complications. The risks and benefits of the use of anticoagulants should be reassessed on a regular basis. For more information regarding the use of anticoagulants, refer to the prescribing information of the anticoagulant and accepted clinical practice guidelines

- For restrictions on oral anticoagulants see Section 9.2.

Potential drug interactions with cabozantinib are summarized in Section 9.3.1.

9.2 Prohibited or Restricted Therapy

The following therapies are prohibited until study treatment has been permanently discontinued:

- Any investigational agent or investigational medical device.
- Oral anticoagulants with coumarin agents (eg, warfarin), direct thrombin inhibitor (e.g., dabigatran), direct factor Xa inhibitor betrixaban, antiplatelet agents such as clopidogrel, or chronic use of aspirin above low dose levels for cardioprotection (per local applicable guidelines) until 4 weeks after cabozantinib has been permanently discontinued.
- Any nonprotocol systemic anticancer treatment (eg, chemotherapy, immunotherapy, radionuclides, drugs or herbal products used specifically for the treatment of the cancer under investigation).
- Systemic corticosteroids above adrenal gland cortisol replacement levels (e.g. > prednisone 7.5 daily or equivalent) at study entry are not permitted. Use of corticosteroids above this level while on study may be required for management of immune related adverse events. Nivolumab and ipilimumab are held/discontinued while patients are on high dose corticosteroids and subsequent taper. Once steroid taper completed, patients may restart nivolumab and/or ipilimumab based on management guidelines in section 8.4. Patients may restart cabozantinib during steroid taper if adverse event is improved to grade 1 or better and management guidelines in section 8.3 are followed.

The following therapies should be avoided until study treatment has been permanently discontinued or until otherwise specified:

- Local anticancer treatment including palliative radiation, ablation, embolization, or surgery with impact on tumor lesions should not be performed until radiographic progression per imRECIST 1.1 has been established.
- Erythropoietic stimulating agents (eg, epoetin alfa and darbepoetin alfa) should not be used based on a report of increased risk of tumor recurrence/progression associated with erythropoietin (Wright et al 2007).
- Concomitant medications that are known to prolong the QTc interval should be avoided in subjects who receive cabozantinib until they have permanently discontinued cabozantinib treatment (refer to <http://www.qtdrugs.org> for a list of drugs which have the potential to prolong the QTc interval).
- Chronic co-administration of cabozantinib with strong inducers of the CYP3A4 family (eg, phenytoin, carbamazepine, rifampin, rifabutin, rifapentine, phenobarbital, and St. John's Wort) may significantly decrease cabozantinib concentrations and should be avoided. Selection of alternate concomitant medications with no or minimal CYP3A4 enzyme induction potential is recommended.
- Caution must be used when discontinuing treatment with a strong CYP3A4 inducer in a subject who has been concurrently receiving a stable dose of cabozantinib, as this could significantly increase the exposure to cabozantinib.

- Co-administration of cabozantinib with strong inhibitors of the CYP3A4 family (eg, boceprevir, conivaptan, posaconazole, ketoconazole, itraconazole, clarithromycin, atazanavir, indinavir, nefazodone, nelfinavir, saquinavir, ritonavir, lopinavir, telaprevir, telithromycin, and voriconazole) may increase cabozantinib concentrations and should be avoided. Grapefruit, star fruit, and Seville oranges may also increase plasma concentrations of cabozantinib and should be avoided.

Additional information on potential drug interactions with cabozantinib is provided in Section 9.3.1.

9.3 Potential Drug Interactions

9.3.1 Potential Drug Interactions with Cabozantinib

Currently available data suggest that cabozantinib: (1) is not anticipated to markedly induce or inhibit CYP enzymes at clinically-relevant plasma concentrations; (2) is a substrate for CYP3A4; (3) may have the potential to inhibit the P-gp transport activity but is not a substrate of P-gp; and (4) is a substrate of drug transporter MRP2.

Cytochrome P450: Cabozantinib is a CYP3A4 substrate and a weak substrate for CYP2C9 (but not a CYP2D6, CYP2C8, CYP2C19, CYP2B6, or CYP1A2 substrate. Co-administration of cabozantinib with strong inducers of the CYP3A4 family (e.g., phenytoin, carbamazepine, rifampin, rifabutin, rifapentin, phenobarbital, and St. John's wort) may significantly decrease cabozantinib concentrations. The chronic use of strong CYP3A4 inducers should be avoided. Other drugs that induce CYP3A4 should be used with caution because these drugs have the potential to decrease exposure (AUC) to cabozantinib. Selection of alternate concomitant medications with no or minimal CYP3A4 enzyme induction potential is recommended. Caution must be used when discontinuing treatment with a strong CYP3A4 inducer in a subject who has been concurrently receiving a stable dose of cabozantinib, as this could significantly increase the exposure to cabozantinib.

Co-administration of cabozantinib with strong inhibitors of the CYP3A4 family (e.g., ketoconazole, itraconazole, clarithromycin, indinavir, nefazodone, nelfinavir, and ritonavir) may increase cabozantinib plasma concentrations. Grapefruit and Seville oranges may also increase plasma concentrations of cabozantinib. Strong CYP3A4 inhibitors and other drugs that inhibit CYP3A4 should be avoided.

Please refer to the drug interaction tables at the following websites for lists of substrates, inducers, and inhibitors of selected CYP450 isozyme pathways:

<http://medicine.iupui.edu/clinpharm/ddis/table.aspx>

<http://www.fda.gov/Drugs/DevelopmentApprovalProcess/DevelopmentResources/DrugInteractionsLabeling/ucm080499.htm>).

Protein Binding: Cabozantinib is highly bound (approximately 99.9%) to human plasma proteins. Therefore, highly protein bound drugs (e.g., diazepam, furosemide, dicloxacillin, and propranolol) should be used with caution with cabozantinib because there is a potential displacement interaction that could increase free concentrations of cabozantinib and/or a co-

administered highly protein bound drug (and a corresponding increase in pharmacologic effect). Factors that influence plasma protein binding may affect individual tolerance to cabozantinib. A case of a drug-drug interaction between cabozantinib and warfarin that may involve displacement of plasma protein bound drug has been reported in the literature (Foxx-Lupo et al. 2016). Because warfarin is a highly protein bound drug with a low therapeutic index, administration of warfarin at therapeutic doses is not allowed in subjects receiving cabozantinib due to the potential for a protein binding displacement interaction.

Food Effects: As food increases exposure levels of cabozantinib, subjects should fast (with the exception of water) for at least 2 hours before taking their dose of cabozantinib. After the 2 hour fast, subjects are to take cabozantinib with a full glass of water (minimum of 8 oz. or 240 mL) with no more food intake for one hour post-dose.

Other Interactions: In vitro data suggest that cabozantinib is unlikely to be a substrate for P-glycoprotein, but it does appear to have the potential to inhibit the P-glycoprotein transport activity. Therefore, cabozantinib may have the potential to increase plasma concentrations of co-administered substrates of P-glycoprotein. Subjects should be cautioned regarding taking a P-gp substrate (e.g., fexofenadine, aliskiren, ambrisentan, dabigatran etexilate, digoxin, colchicine, maraviroc, posaconazole, ranolazine, saxagliptin, sitagliptin, talinolol, tolvaptan) while receiving cabozantinib. Additional details related to these overall conclusions can be found in the investigator brochure.

Administration of the proton pump inhibitor (PPI) esomeprazole resulted in no clinically-relevant effect on cabozantinib plasma PK in healthy volunteers. Therefore, concomitant use of gastric pH modifying agents (ie, PPIs, H₂ receptor antagonists, and antacids) is not contraindicated in subjects administered cabozantinib. Additional details regarding potential drug interactions with cabozantinib can be found in the investigator brochure.

Cabozantinib was shown to be a substrate of drug transporter MRP2 in an in vitro assay. Administration of MRP2 inhibitors to subjects may result in increases in cabozantinib plasma concentrations. Therefore, concomitant use of MRP2 inhibitors (e.g., cyclosporine, delaviridine, efavirenz, emtricitabine) should be approached with caution, and subjects taking MRP2 inhibitors should be monitored for AEs.

9.3.2 Potential Drug Interactions with Nivolumab and Ipilimumab

There are no specific drug-drug interactions with nivolumab and ipilimumab and other drugs. Based on the mechanism of action, these agents are usually held during courses of high dose corticosteroids and patients requiring immune suppression for organ transplant, autoimmune disorders and other disease are not permitted to participate on this protocol.

9.4 Study Treatment Accountability

The investigator or designee will maintain accurate records of receipt of all study treatment including dates of receipt. In addition, accurate records will be kept regarding the date, lot number, and how much study treatment is dispensed and used by each subject in the study. Reasons for deviation from the expected dispensing regimen must also be recorded. At completion of the study, to satisfy regulatory requirements regarding drug accountability, all

unused study treatment will be reconciled and destroyed according to applicable state, federal, and local regulations.

10 SAFETY

10.1 Adverse Events and Laboratory Abnormalities

10.1.1 Adverse Events (AEs)

An AE is any untoward medical occurrence in a patient or clinical trial subject administered a medicinal product and which does not necessarily have a causal relationship with this treatment. An adverse event can therefore be any unfavorable and unintended sign (e.g. an abnormal laboratory finding), symptom, or disease temporarily associated with the use of a medicinal product, whether or not considered related to the medicinal product. An adverse event can arise from any use of the drug (e.g. off-label use, use in combination with another drug) and with any route of administration, formulation, or dose, including an overdose. This definition also includes AEs associated with medication errors and uses of the investigational product outside what is in the protocol, including misuse and abuse. Pre-existing medical conditions that worsen during the study should be recorded as AEs. Abnormal laboratory values, ECG findings, or vital signs are to be recorded as AEs if they meet the criteria described in this protocol. All untoward events that occur after informed consent through 30 days after the decision to discontinue study treatment (or the date the subject is deemed to be a screen failure) are to be recorded by the investigational site. This requirement includes AEs from unscheduled as well as scheduled visits and includes the new onset of or increase in pain during this period.

Adverse event terms recorded on the CRFs will be mapped to preferred terms using the Medical Dictionary for Regulatory Activities (MedDRA). Seriousness, severity grade, and relationship to study treatment will be assessed by the investigator. Severity grade will be defined by the current version of the National Cancer Institute (NCI)-Common Terminology Criteria for Adverse Events (CTCAE).

10.1.2 Serious Adverse Events (SAEs)

The SAE definition and reporting requirements are in accordance with the International Conference of Harmonisation (ICH) Guideline for Clinical Safety Data Management: Definitions and Standards for Expedited Reporting, Topic E2A.

An SAE is defined as any untoward medical occurrence that at any dose:

- Result in death;
- Is life-threatening (i.e., in the opinion of the investigator, the AE places the subject at risk of death; it does not include an event that, had it occurred in a more severe form, might have caused death);
- Requires inpatient hospitalization or results in prolongation of an existing hospitalization;
 - Note: While most hospitalizations necessitate reporting of an SAE, some hospitalizations do not require SAE reporting, as follows: elective or previously scheduled surgeries or procedures for pre-existing conditions that have not worsened after initiation of treatment (e.g., a previously scheduled ventral hernia repair); pre-specified study hospitalizations for observation; or events that result

in hospital stays of fewer than 24 hours and that do not require admission (e.g., an ER visit for hematuria that results in a diagnosis of cystitis and discharge home on oral antibiotics). SAEs must, however, be reported for any surgical complication resulting in prolongation of the hospitalization.

- Results in persistent or significant disability or incapacity:
 - Note: The term “disability” refers to events that result in a substantial disruption of a subject’s ability to conduct normal life function.
- Is a congenital anomaly or birth defect;
- Is an important medical event (IME):
 - Note: The term “important medical event” refers to an event that, based upon appropriate medical judgment, may not be immediately life-threatening or result in death or hospitalization, but may jeopardize the subject or require intervention to prevent one of the other serious outcomes listed. Examples of IMEs include intensive treatment in an emergency room or at home for allergic bronchospasm; blood dyscrasias, or convulsions that do not result in hospitalization; or development of product dependency or product abuse.

10.1.3 Relationship to Study Treatment

Assessment of the relationship of the AE to the study treatment by the investigator is based on the following two definitions:

- Not Related: A not-related AE is defined as an AE that is not associated with the study treatment and is attributable to another cause or there is no evidence to support a causal relationship;
- Related: A related AE is defined as an AE where a causal relationship between the event and the study treatment is a reasonable possibility. A reasonable causal relationship is meant to convey that there are facts (e.g., evidence such as dechallenge/rechallenge) or other clinical arguments to suggest a causal relationship between the AE and study treatment. Possibly and probably related AEs should be documented as related.

10.1.4 Serious Adverse Event Reporting

As soon as an investigator becomes aware of an AE that meets the definition of ‘serious,’ this must be documented on an SAE Report Form or in an electronic database and include the following: (i) all SAEs that occur after starting cabozantinib and through 30 days after the decision to discontinue study treatment and (ii) any SAEs assessed as related to study treatment or study procedures, from the time of informed consent, even if the SAE occurs more than 30 days after the decision to discontinue study treatment.

All SAEs and all pregnancy/lactation reports regardless of outcome must be sent to Exelixis within one (1) business day of the PI’s knowledge of the event. The reports must be sent to

- The PI will perform adequate due diligence with regard to obtaining follow-up information on incomplete reports. All follow-up information must be sent to Exelixis within one (1) business day of the PI’s receipt of the new information. Upon Exelixis request, the PI will query for follow-up information.

Serious adverse events will also be reported, and all supporting documentation sent (emailed) to the Multicenter Project Manager(s) and to the study PI, [name], within 24 hours.

10.1.5 Regulatory Reporting

The Investigator will assess the expectedness of each related SAE. The current cabozantinib Reference Safety Information (Appendix K of the most recent approved Investigator Brochure) will be used as the reference document for assessing the expectedness of the event with regard to cabozantinib. Current package inserts for nivolumab and ipilimumab should be referenced as well. All serious unexpected adverse drug reactions (unexpected related SAEs) must be reported to all appropriate regulatory authorities and Ethics Committees by the investigator as required by 21 CFR 312.32 or by Directive 2011/20/EC:

- These reports are to be filed utilizing the Form FDA 3500A (MedWatch Form) or a CIOMS-1 form;
- Exelixis reserves the right to upgrade the Investigator assessment of an SAE based on Exelixis assessment.
- Institutions and PIs shall promptly provide all information requested by Exelixis regarding all adverse events occurring during the conduct of the study.
- The PI is responsible for complying with all regulatory authority reporting requirements for the study that are applicable to the sponsor of a clinical trial. The PI shall provide a copy of all responses to regulatory agency requests, periodic reports, and final study reports to Exelixis within one (1) business day of the submission.
- Exelixis will provide relevant product safety updates and notifications, as necessary. In the case of multi-center studies, it is the responsibility of the sponsoring PI/Institution to disseminate these updates to participating PIs.

10.2 Other Safety Considerations

10.2.1 Laboratory Data

All laboratory data required by this protocol and any other clinical investigations should be reviewed. Any abnormal value that leads to a change in subject management (e.g., dose reduction or delay or requirement for additional medication or monitoring) or that is considered to be of clinical significance by the investigator should be reported as an AE or SAE as appropriate.

10.2.2 Pregnancy/Lactation Exposure

If a subject becomes pregnant during the study, she will be taken off study treatment and will be followed through the end of her pregnancy. Pregnancy (in subject or partner) or lactation exposure, although not an SAE, should be reported to Exelixis. Forms will be provided to the study sites upon request. The outcome of a pregnancy (for a subject or for the partner of a subject) and the medical condition of any resultant offspring must be reported to Exelixis. Any birth defect or congenital anomaly must be reported as an SAE, and any other untoward events occurring during the pregnancy must be reported as AEs or SAEs, as appropriate.

10.2.3 Medication Errors/Overdose

Any overdose, or study drug administration error that results in an AE, even if it does not meet the definition of serious, requires reporting within one (1) business day to Exelixis.

10.2.4 Follow-Up of Adverse Events

Any related SAEs or any AEs assessed as related that led to treatment discontinuation, including clinically significant abnormal laboratory values that meet these criteria, ongoing 30 days after the decision to discontinue study treatment must be followed until either resolution of the event or determination by the investigator that the event has become stable or irreversible. This follow-up guidance also applies to related SAEs that occur more than 30 days after the decision to discontinue study treatment. The status of all other continuing AEs will be documented as of 30 days after the decision to discontinue study treatment.

11 STATISTICAL CONSIDERATIONS

Simon's Two-Stage Design will be used in hypothesis testing for the primary endpoint of a 1 year PFS rate. Based on the Checkmate 067 data [1], a 1 year PFS rate in the historical control is assumed to be 50% (H0: PFS rate=50%). In this trial, a target 1 year PFS rate will be 75% (improvement by 25%, H1: PFS rate \geq 75%), which is deemed a clinically meaningful improvement. This will require a sample size of 23 for a one sided alpha of 0.05 and the power of 0.80. In the futility stage with the first 14 subjects, the study will be stopped if there are 7 or fewer subjects progression free at 1 year. In the final analysis, the null hypothesis will be rejected if 16 subjects or more are progression free at 1 year of the 23 total subjects. Assuming a dropout rate of 15% during the time of study, up to 27 subjects will be enrolled.

In the event of unplanned interim analyses are needed due to slow accrual or any other reasons, we will use the curtailing based SCPRT approach for statistical analysis [36].

The PFS rate in the final analysis will be calculated and a 2-sided Clopper–Pearson 95% confidence interval (CI) will be calculated. PFS and OS will be analyzed using Kaplan–Meier product-limit estimates. Median PFS and OS and the cumulative probability of PFS and OS will be presented with two-sided 95% CI if estimable.

Remaining analyses will be descriptive and exploratory in nature. TMB will be evaluated as a continuous variable and dichotomous breakdowns including previously reported high vs low status using a 21 nonsynonymous variants/MB cutoff [37]. PD-L1 status will use high/low cutoffs of 1% and 5% positive IHC rates [1]. Other variables will be analyzed based on published data or optimization of cutoffs. Statistical comparisons will be performed with SAS/R and looking to determine associations with biomarkers and clinical outcomes.

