	
localized, low grade tumors deemed cured and not treated with systemic therapy.
 
16. Subjects with a condition requiring systemic treatment with either corticosteroids (> 10 mg daily prednisone equivalents) or other immunosuppressive medications within 14 days of study drug administration. Inhaled or topical steroids, and adrenal replacement doses > 10 mg daily prednisone equivalents are permitted in the absence of active autoimmune disease.

STATISTICAL CONSIDERATIONS	
The primary endpoint for the study is 1 year landmark PFS rate. The historical control with nivo/ipi from the Checkmate 067 study is a 1 year PFS rate of ~50% [1]. The target for this study is 75% (improvement by 25%), which is deemed a clinically meaning improvement. This will require a sample size of 23 for a one sided alpha of 0.05 and the power of 0.80. A simon two stage approach will be utilized. The study will be stopped if there 7 or few subjects out of 14 subjects progression free at 1 year. If the study meets criteria for continuation to the second stage, an additional 9 subjects will be enrolled. In the final analysis, the null hypothesis will be rejected (i.e., accept the alternative hypothesis of improved efficacy with nivolumab/ipilimumab plus cabozantinib) if 16 subjects or more are progression free at 1 year of the 23 total subjects. Assuming a dropout rate of 15% during the time of study, up to 27 subjects will be enrolled.

TOTAL NUMBER OF SUBJECTS	27 enrolled subjects (23 subjects required for primary endpoint analysis)
ESTIMATED ENROLLMENT PERIOD	Estimated 18 months
ESTIMATED STUDY DURATION	Estimated 42 months (2 years beyond last patient enrolled)

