7.5 Treatment Response Assessment

Only those subjects who have measurable disease present at baseline, have received at least one dose nivolumab, ipilimumab and cabozantinib, and had one on-treatment scan or progressed clinically will be considered evaluable for response. These subjects will have their response classified according to the definitions stated below. Those subjects that are not evaluable for response will be replaced. Immune-Modified Response Evaluation Criteria in Solid Tumors (imRECIST) will be used for the primary response assessment and for progression free survival determination [33]. Best overall response rate will be reported. Start of treatment will define the start date for calculations of PFS and OS.

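### The stated power of 0.80 holds only without progression-free loss before 1 year; under the plan's 15% dropout it is about 0.73 to 0.79, depending on when loss occurs

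*Combined protocol and SAP*

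**What the plan says.** Section 11 (Statistical Considerations) tests a 1-year PFS rate of 50% against a target of 75% with a Simon two-stage count. On size it states: "This will require a sample size of 23 for a one sided alpha of 0.05 and the power of 0.80". At the first 14 subjects, "the study will be stopped if there are 7 or fewer subjects progression free at 1 year". At the end, "the null hypothesis will be rejected if 16 subjects or more are progression free at 1 year of the 23 total subjects". It then adds: "Assuming a dropout rate of 15% during the time of study, up to 27 subjects will be enrolled". The synopsis gives the same pair of numbers: "27 enrolled subjects (23 subjects required for primary endpoint analysis".

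The final rate is to be reported with a Clopper-Pearson interval. Kaplan-Meier estimates of PFS are also planned, but the decision rests on the count.

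The only written rule on replacing subjects is in Section 7.5. It covers subjects not evaluable for response, and a subject who received all three drugs and "had one on-treatment scan or progressed clinically will be considered evaluable for response". No section says how a subject who leaves progression free after that scan but before 1 year enters the count. Nor does the plan give the period of the 15% beyond the time of study, which the synopsis puts at an estimated 42 months.

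**The concern.** The step from 27 to 23 treats dropout as if it removed subjects at random with respect to outcome. It does not. A subject who progresses and then leaves is already a known failure and stays in the count. A subject who leaves progression free has no 1-year status and drops out of it. The subjects removed would mostly have been successes, together with some later failures. Extra enrolment restores the number counted but not the success probability among them.

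The design has almost no slack, so any fall in the counted rate takes power below the stated figure. What is at stake is a higher chance of missing a true 75% rate, and a primary estimate that is too low.

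**Working it through.** **Inputs.** From Section 11: null 0.50, target 0.75, stage 1 of 14 (stop at 7 or fewer), total 23 (reject at 16 or more), dropout 15%, up to 27 enrolled. From the synopsis: 42 months' duration. Assumed here: constant hazard, so S(t) = p^t with t in years; non-informative loss, uniform over the period named; exactly 23 known statuses reached.

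**Step 1: the plan's own figure.** Power = sum over x = 8 to 14 of P(Bin(14, p) = x) × P(Bin(9, p) ≥ 16 − x). At p = 0.75 the terms are 0.0220 + 0.0882 + 0.1837 + 0.2285 + 0.1784 + 0.0830 + 0.0178 = 0.8016. At p = 0.50 the sum is 0.0462. Both stated figures reproduce. The inflation is 23 / 0.85 = 27.06, and 27 × 0.85 = 22.95.

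**Step 2: the counted rate.** Let q be the probability of loss in year 1, spread over (0, T) with T ≤ 1, and m = (1 − p^T) / (−T ln p) the mean of S over that period.
- Known successes: p(1 − q)
- Lost progression free: q × m
- Counted rate: r = p(1 − q) / (1 − q × m)

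Where the 15% is spread over more than a year, the year-1 share is q = 0.15 / years, with T = 1.

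**Step 3: 15% lost evenly over year 1, p = 0.75.** m = 0.25 / 0.2877 = 0.869.
- If 15% is the chance of leaving whether or not progression has come first: r = 0.6375 / (1 − 0.1304) = 0.733.
- If 15% are actually lost progression free: q = 0.15 / 0.869 = 0.1726, and r = 0.75 × 0.8274 / 0.85 = 0.730.

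**Step 4: put r into the Step 1 formula.** All rows but the second use the first definition of the 15%.

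| Timing of the 15% | r at true 75% | Power | r at true 50% | Type I error |
|---|---|---|---|---|
| Evenly over year 1 | 0.733 | 0.744 | 0.477 | 0.028 |
| Evenly over year 1, 15% observed lost progression free | 0.730 | 0.733 | 0.466 | 0.022 |
| First 6 months | 0.741 | 0.772 | 0.487 | 0.035 |
| First 12 weeks | 0.746 | 0.788 | 0.493 | 0.040 |
| Over 2 years (q = 0.075) | 0.742 | 0.776 | 0.489 | 0.037 |
| Over 42 months (q = 0.15 / 3.5 = 0.043) | 0.746 | 0.787 | 0.494 | 0.041 |

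The extremes for 15% observed lost progression free are 0.80 if all leave at day 0, and 0.64 if all leave just before 1 year (r = (0.75 − 0.15) / 0.85 = 0.706).

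**Step 5: bias of the crude proportion.** With loss over year 1 it is 0.75 − 0.733 to 0.75 − 0.730, about 2 points, at a true 75%. At a true 50% it is 0.50 − 0.477 to 0.50 − 0.466, or 2.3 to 3.4 points.

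**The case against.** The best defence has four parts.

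- **Exclusion is inferred, not written.** This stands as a limit on the wording. But if dropouts were counted as failures among 23, the rate would be 0.75 × 0.85 = 0.6375 and power 0.36, and there would be no reason to enrol 27 to keep 23. Exclusion is the handling that makes the two numbers fit.
- **The timing is open.** The 15% is tied to the time of study, and some of it may be early loss before the first scheduled on-treatment scan at week 13, which Section 7.5 replaces. A reader might infer that power simply is 0.73. The documents do not support that: it is the result for one timing, and others give up to 0.79. Against the longest reading, 15% over 42 months loses only about 27 × 0.037 = 1 subject progression free in year 1, so 27 would not be needed to retain 23. Every timing tabulated is still below 0.80.
- **Nothing is miscalculated.** A reader might infer an arithmetic error. There is none: 0.80 is right for 23 subjects at 75%, and quoting power for evaluable subjects before inflating enrolment is common practice. The gap is between that power and the dropout stated beside it.
- **The bias is conservative.** True. A positive result is no less credible, and a 2-point shift is small beside an exact interval on 23 subjects. The cost falls on power and on the estimate.

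**Conclusion.** The concern holds in conditional form. Power of 0.80 applies if no subject is lost progression free before 1 year (or if all loss falls at day 0). If such subjects are left out of the count, as the step from 27 to 23 implies, power at a true 75% is about 0.73 to 0.74 with 15% lost evenly in year 1. It is about 0.77 to 0.79 if the loss is early or spread over 2 to 3.5 years. The chance of missing a true 75% rate thus rises from about 20% to between 21% and 27%. Type I error falls from 0.046 to about 0.02 to 0.04. The crude proportion and its interval are shifted down by up to about 2 points at 75% and 3 points at 50%.

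These figures rest on constant hazard, non-informative loss and exactly 23 known statuses. The direction of the bias does not depend on the constant hazard. No other section removes the problem, because a subject lost progression free after the first on-treatment scan is neither replaced nor given a 1-year status.

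**What to change.** In Section 11 and the synopsis:

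1. State that power 0.80 applies with no progression-free loss before 1 year. State the period that the 15% covers, and give power under it (about 0.73 to 0.79 by timing).
2. State how subjects lost progression free before 1 year are counted, both at the 14-subject stage and at the end.
3. Report the 1-year PFS rate and its confidence interval from the already planned Kaplan-Meier estimate in all treated subjects, not only from the crude proportion.

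Moving the final test to Kaplan-Meier is optional. If it is done, pre-specify one test that applies whether or not anyone is lost. Switching tests on observed loss would leave the combined error rates unknown. Report its type I error and power with the stage 1 rule included. By simulation, requiring the one-sided 95% log-log lower limit to exceed 50% in 27 subjects with 15% loss gives about 0.04 and 0.78 before the stage 1 stop, so this does not fully restore 0.80 either.

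Cost: the stated power becomes less favourable, and the wording needs an amendment under Section 15. No patients are added.
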